1. The use of the prohibited therapy indicated above, specific to each of the groups.
2. Withdrawal of informed consent.
3. Compliance to the study therapy is 50% or less.
4. Systematic non-compliance with protocol procedures by the participant.
5. Development of individual intolerance to the study drug (for the study group).
6. The development of concomitant diseases or conditions that, according to the researcher, may distort the results of the study, restrict the rights of the volunteer or put him at greater risk.
7. The appearance of contraindications to the use of the study drug in the period before the last intake of the second 10-day cycle (for the study group).
8. Participation in a clinical trial using a different therapy.
9. Disagreement on following reliable contraceptive measures (sexual abstinence; or a combination of 2 different methods: for example, barrier and spermicides, or barrier and intrauterine device, or barrier and hormonal, etc.) – for participants with preserved childbearing potential in the period before the last intake of the second 10-day cycle (for the study group).
10. Pregnancy.

A woman who excluded from the study due to the onset of pregnancy during the clinical trial is subject to medical supervision during the entire period of pregnancy, as well as for 6 months postpartum period to assess the condition of the woman and the born child (observation is carried out if possible and only if her desire and consent to such observation is mandatory). Information about the course of pregnancy and its outcome is entered in the primary documentation (with the consent of the woman). During the entire period of pregnancy, together with an obstetrician-gynecologist (with the consent of the pregnant woman and, if possible, contact with a doctor), observing a woman, her general condition, data reflecting the nature of the course of pregnancy, results of laboratory and instrumental examination methods, including ultrasound, are analyzed. Monitoring of the born child is carried out with the consent of the woman together with the district pediatrician (if possible, contact with him) until the child is 6 months old to analyze the clinical status of the child, data from laboratory and instrumental research methods.

There are no procedures for replacing excluded participants.

Diaries of participants

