Address of the place of manufacture: [name], J.S.C. "Biomed"-Mechnikov Tel/[contact], [name]

E-mail: [contact] Internet: www.pharmaclon.ru

Labelling: The inscription "For post-marketing research RAIN-2020" is applied to the primary packaging and secondary (consumer) packaging of the study drug product, the inscription "Not for sale" is additionally applied to the secondary (consumer) packaging in accordance with the requirements of the Federal Law "On Circulation of Medicines" dated 12.04.2010 N 61-FZ as amended Federal Law No. 429-FZ from 22.12.2014.

Compliance assessment

Assessment of compliance with study preventive therapy is evaluated on the basis of data recorded in the participant's diary, on visit 3, as well as in advance as part of an oral survey of the participant on a phone call visit after the end of preventive use of the drug. Compliance is assessed on a 100% scale, where:

100% – participant completed 2 cycles of 10-day courses without violating the dosage regimen and the frequency of admission

90% – participant completed 2 cycles of 10-day courses with a single violation of dosage regimen or dosage frequency

80% – participant completed 1 cycle of the 10-day course without violating dosage regimen or dosage frequency

70% – participant completed 2 cycles of 10-day courses with a double violation of dosage regimen or dosage frequency (single violation of each course)

60% – participant completed 1 cycle of 10-day course with a single violation of dosage regimen or dosage frequency

50% or less – participant completed 1 or 2 cycles of 10-day courses with a systematic (twofold or more) violation of the dosage regimen or dosage frequency in each of the courses (non-compliance with a single dose, frequency of use and/or its duration).

Compliance of 50% or less is the criterion for excluding a participant from the study.

STUDY PARAMETERS OF EFFICIENCY AND SAFETY

Effectiveness criteria

Effectiveness criteria will be evaluated according to the data recorded in the participants' diaries, in primary medical documentation.

Primary effectiveness criterion:

The proportion of patients with acute respiratory viral infections, including COVID-19, at the end of the period of preventive administration of the drug (measurement time: 28 days).

Secondary effectiveness criterion:

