4. Open the vial of water for injection by breaking off its upper part.
5. Pour 5 ml of water for injection into glass vial with a dry substance.
6. Remove the dropper cap from the package and fix it on the neck of the bottle.

Due to the need to store the active substance in a full vacuum, the aluminum cap must be hermetic and durable. Slowly remove the aluminum guard of the bottle, avoid cuts. If the cap breaks off during removal, you can remove the rest of the metal cap with scissors.

Take vial with Ingaron with liquid inside with both hands and turn it over 10–15 times.

Put the vial with Ingaron with the liquid inside in the refrigerator and store there for 10 days. For the second course of prevention (after 1 week), use the second vial.

Return the empty ampoules of water for injection together with the used glass vials to the researcher at the next visit.

Administration

Course 1. The drug is applied 3 drops in each nasal passage every other day 30 minutes before breakfast for 10 days (total of 5 instillations). The use of the drug is carried out according to the following regimen:

- Course 1. Day 1 – mark administration time in your diary
- Course 1. Day 3 – mark administration time in your diary
- Course 1. Day 5 – mark administration time in your diary
- Course 1. Day 7 – mark administration time in your diary
- Course 1. Day 9 – mark administration time in your diary

This is 1 preventive cycle. Then a break of 7 days.

Course 2. Drug administration is carried out similarly to Course 1. Preparation of the drug is carried out similarly to the algorithm described earlier. Dosage regimen is the same:

- Course 2. Day 1 – mark administration time in your diary
- Course 2. Day 3 – mark administration time in your diary
- Course 2. Day 5 – mark administration time in your diary
- Course 2. Day 7 – mark administration time in your diary
- Course 2. Day 9 – mark administration time in your diary

If you missed drug administration, mark the day in your diary with a "check mark" and take the next dose the next morning 30 minutes before breakfast and then continue using it every other day. Remember that the finished solution of the drug is stored for no more than 10 days in the refrigerator. Do not use it after the expiration date. For Course 2, use the second bottle, do not use the first bottle, even if the drug is not fully used.

| | |
|---------------------------------|---|
| Course 1 Day 1 | Date ____ ____ ____ ____ ____ ____ day month year |

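### The compliance scale does not follow the 10 planned instillations, so its 50% cut can keep a study-group participant with 4 or 5 and exclude one with 6 or more

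*Protocol*

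**What the plan says.** The study-group diary (Protocol, Appendix 1, Administration) gives Course 1 a "total of 5 instillations", on days 1, 3, 5, 7 and 9, and continues: "Course 2. Drug administration is carried out similarly to Course 1". After a missed day the participant is told to instil the next morning and then go on every other day. The prepared solution may be kept for no more than 10 days.

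Protocol, Compliance assessment, grades adherence in fixed levels. Both cycles taken score 100% if faultless and 90% after one slip. The next level down reads "80% – participant completed 1 cycle of the 10-day course without violating dosage regimen or dosage frequency". Beneath that, taking both cycles with one slip per course earns 70%, and taking just one cycle with one slip earns 60%. The lowest level, 50% or less, is for at least two slips in each course, whether one course was taken or both. A slip may lie in the amount instilled, the timing or the length of use.

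Protocol, Exclusion criteria, item 3, removes a participant from the study when "Compliance to the study therapy is 50% or less". Compliance assessment repeats the rule.

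The SAP (5.5) defines ITT without regard to how closely the protocol was followed and makes it the main set. PP is additional and takes participants who saw the prescribed treatment and follow-up through with no significant deviation. SAP 5.3 uses available data only.

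**The concern.** A compliance score should not fall as exposure to the planned course rises. Here a participant who never takes the second cycle outranks one who takes both with a slip in each. More importantly, the score feeds an exclusion rule, so participants on the wrong side of the cut leave the study.

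Two things are at stake. PP is the SAP's sensitivity check on ITT, and the 50% rule is the only numeric adherence criterion in either document. In addition, the exclusion is from the study and not merely from PP. The control group takes no study drug, so only Group I can meet the criterion, and any outcomes lost after exclusion are lost in one arm.

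**Working it through.** **Inputs.** 5 instillations per course and 2 courses (Appendix 1); score levels (Compliance assessment); cut at 50% or less (Exclusion criteria, item 3); next-morning rule and 10-day solution life (Appendix 1).

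**Planned total.** 2 × 5 = 10 instillations.

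**Step 1: each violation is one lost dose.** Instillations taken = 5 × cycles − violations, and share = taken / 10.

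- 100% level: 10 − 0 = 10, share 100%. Reproduced.
- 90% level: 10 − 1 = 9, share 90%. Reproduced.
- 80% level: 5 − 0 = 5, share 50%. Not reproduced.
- 70% level: 10 − 2 = 8, share 80%. Not reproduced.
- 60% level: 5 − 1 = 4, share 40%. Not reproduced.

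**Step 2: other kinds of violation.** Under the next-morning rule, one missed day still gives 5 instillations in a course (for example days 1, 4, 6, 8, 10). Two missed days give 4 (for example days 1, 4, 7, 9). A wrong number of drops loses no instillation.

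| Level | Dose lost | Next-morning rule | Drop-count error | Result |
|---|---|---|---|---|
| 100%: two cycles, no violation | 10 | 10 | 10 | kept |
| 90%: two cycles, one violation | 9 | 10 | 10 | kept |
| 80%: one cycle, no violation | 5 | 5 | 5 | kept |
| 70%: two cycles, one in each | 8 | 10 | 10 | kept |
| 60%: one cycle, one violation | 4 | 5 | 5 | kept |
| 50% or less: two cycles, two in each | 6 | 8 | 10 | excluded |
| 50% or less: one cycle, two violations | 3 | 4 | 5 | excluded |

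In every column the 70% row has more instillations than the 80% row, and the excluded two-cycle row has more than both one-cycle rows that are kept.

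**Step 3: is it a penalty score instead?** The first violation costs 10 points (100 to 90), the second 20 (90 to 70), and one within a single cycle 20 (80 to 60). Omitting a whole cycle of 5 instillations also costs 20 (100 to 80). No fixed price per violation and per cycle gives these levels, and a missing cycle costs less than one slip in each course (100 to 70, or 30).

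**Step 4: coverage.** Count instillations taken in each course as 0 to 5, giving 6 × 6 = 36 patterns, with each missed dose a violation. No level describes one course with 0 or 1 missed (2 options) alongside a second, started course with 2, 3 or 4 missed (3 options), in either order: 2 × 3 × 2 = 12 patterns, with 5 to 8 instillations in total. Two violations in one cycle and none in the other is an example.

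**Step 5: against the analysis sets.** The prescribed course is 27 days (10 + 7 + 10; SAP 2.1). A participant who stops after one cycle scores 60% or 80% and passes item 3, yet may fail the SAP's PP definition for not finishing the prescribed treatment. Neither document's PP definition mentions the score. Conversely, someone excluded under item 3 still belongs in ITT by definition, but later outcomes may not be collected and are not filled in.

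**The case against.** The strongest defence is that the scale never claims to be a dose fraction. It grades adherence to a regimen, and the product information describes a single 10-day course, so generous credit for one clean course may be deliberate. A pure count would also give full marks to someone who used the wrong number of drops throughout. The second point stands and shapes the fix. The first explains the 80% level but not the ordering: the study regimen is two cycles, and step 3 shows that the levels are not a consistent penalty score either.

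If one cycle is read to include a second cycle started with two or more misses, the 12 unscored patterns find a place: the 80% level then covers 5 to 8 instillations and the 60% level 4 to 7. The text does not say this, and a participant with 4 or 5 could still be kept while one with 6 is removed.

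A reader might infer four stronger things that the documents do not support:

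- **The 80%/70% inversion itself misdirects exclusions.** It does not, since both levels are above the cut.
- **The figures 8, 4 and 6 of 10 are exact.** They hold only if every violation is a lost dose.
- **PP will certainly contain half-course participants.** The SAP wording may already bar them, so this is a conflict to settle.
- **About 31 of 315 (10%) in Group I are affected.** That allowance covers all premature exclusion and consent withdrawal. It does not bound compliance exclusions, and it cannot count low-exposure participants who are kept.

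The diary point also has limits. Its even-day pages show no field for administration time, and catch-up doses after a single missed day fall on those days. But the protocol (Diaries of participants) promises a calendar of instillation days, and part of the appendix is not readable here.

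**Conclusion.** The compliance levels are non-monotone and, as worded, incomplete against the 10 planned instillations. At the 50% cut, 4 to 5 instillations can be kept (60% level) while 6 are excluded if doses are lost, 8 under the next-morning rule, and up to 10 if the violations are drop-count errors. The direction of the missorting does not depend on which kind of violation is assumed; only its width does.

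The rule acts on Group I alone, on the inference that a group without study drug cannot fail it. It leaves PP membership of one-cycle participants unsettled and can remove later outcomes from one arm.

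The number affected is unknown. The effect on the 28-day ITT analysis is probably small: compliance is first assessed at the end-of-course telephone visit (day 27 ± 3 in the schedule), where exclusion criteria are also checked. The two-month endpoints and PP are more exposed. This should be corrected, but it does not threaten the main analysis.

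**What to change.** Reconcile the scale, item 3 and the SAP's PP definition as follows.

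1. Define compliance as instillations taken divided by 10, from the diary and its calendar, and let the diary accept an administration time on any day.
2. Record dose and timing errors separately as protocol deviations, and state in the SAP how they bear on PP.
3. Apply the sponsor's existing 50% cut-off to this figure, and use it only to define PP. With that cut, 4 of 10 and 5 of 10 fall at or below it, and 6 of 10 and 8 of 10 lie above it. One-cycle participants then fall outside PP under both documents.
4. Keep participants at or below the cut in follow-up and in ITT.

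The cost is a wording change in protocol and SAP, a small diary change and one derived variable.

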- to evaluate the safety of the proposed regimen of preventive therapy with Ingaron (INN: human recombinant interferon gamma, lyophilizate for the preparation of solution for intranasal administration of 100,000 IU) in adult volunteers. Safety is assessed based on adverse events, clinically significant changes in laboratory parameters during the study, taking into account the assessment of severity according to the STCAE 4.03 scale.

OBJECTIVES OF NON-INTERVENTIONAL RESEARCH

Primary objective

To evaluate the effectiveness of the prophylactic use of Ingaron (INN: human recombinant interferon gamma, lyophilizate for the preparation of solution for intranasal administration of 100,000 IU) in the mode of 3 drops in each nasal passage intranasally every other day for 10 days with break of 7 days (2 10-day cycles) in adult volunteers.

Secondary objectives

Safety assessment of the prophylactic use of Ingaron (INN: human recombinant interferon gamma; lyophilizate for the preparation of a solution for intranasal administration of 100,000 IU), applied 3 drops into each nasal passage intranasally every other day for 10 days with break of 7 days (two 10-day cycles) in adult volunteers.

Efficacy and safety include evaluation based on epidemiological, anamnestic, and clinical data, as well as laboratory studies and specialized scales.

DESIGN OF A NON-INTERVENTIONAL STUDY

Post-marketing prospective randomized open-label comparative non-interventional study in parallel groups.

A total of 4 visits are planned (0–3). Visit 0 and 1 can be combined.

Main stages of the study

1. Visit 0. Conducted in person⁷. Screening: informed consent, inclusion of volunteers and distribution into groups (Day -3-1)
2. Visit 1. Conducted in person. Randomization. Delivery of the investigated drug and the diary of the researcher participant (Day 0)
3. Visit 2. It is carried out remotely (by phone). Completion of a preventive course, evaluation of preventive efficacy and safety during the period of drug administration. The beginning of the observation period. (Day 28–30)
4. Visit 3. Conducted in person. Completion of the observation and research period. (Day 56–62)

The main procedures and stages of the study are reflected in the Schedule of research procedures.

The total duration of participation is about 2 months (56–62 days).

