For participants who have a case of ARVI (COVID-19), visit 3 can be carried out earlier or later, but the total duration of the study should not be more than 90 days. Up to this point, medical researcher should try to collect the most complete information about the patient's condition. If it is not possible to conduct a face-to-face visit, final visit is conducted remotely.

Schedule of research procedures

| Visit number | 0 | 1 | 2 | 3 |
|---|-----------|---------------|--|--|
| Setting | In person | In person | Phone call | In person |
| Visit name | Screening | Randomization | The end of the course of prevention Beginning of the observation period | End of the observation period Completion of the study |
| Study days | -3-1(0) | 0 | 27 (+/-3) | 56-62* |
| Informed consent ¹ | + | | | |
| Anamnesis ² | + | | | |
| Complaints | + | + | + | + |
| Physical examination ³ | + | + | | + |
| Pregnancy test | + | | | |
| Safety assessment | + | + | + | + |
| Analysis for RNA to SARS-CoV-2 ⁴ | + | | | + |
| Checking the inclusion/non-inclusion criteria | + | + | | |
| Checking exclusion criteria | | | + | |

⁷ A full-time visit can be carried out both at the research center and at home

| | | | | |
|--|---|---|---|----------------|
| Randomization | | + | | |
| Delivery of the study drug ⁵ | | + | | + |
| Compliance assessment | | | + | + |
| Issue of the participant's diary | | + | | |
| Effectiveness evaluation | | | + | + |
| Assessment of the participant's condition according to the WHO scale | + | + | + | + ⁷ |
| Return of study drug and diary | | | | + |

* For patients with a registered case of ARVI, duration of participation in the study may be longer, but not exceed 90 days

- 1 All research procedures, except routine laboratory and instrumental studies, the data of which are used to assess the condition of the study participant, are performed after the procedure of signing the informed consent of the patient
- 2 The study should indicate the epidemiological history of respiratory viral diseases, status of vaccination (influenza, pneumonia, COVID-19), use of means of nonspecific protection and prevention of acute respiratory viral infections, including COVID-19

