1. The proportion of patients with confirmed COVID-19 at the end of the period of preventive treatment of the drug (measurement period: 28 days).
2. The proportion of patients with acute respiratory viral infections, including COVID-19, at the end of the follow-up period (change period: 2 months).
3. The proportion of patients with confirmed COVID-19 at the end of the follow-up period (change period: 2 months).
4. Frequency of development of complicated course of ARVI.
5. The proportion of participants with each of the scores (0-8) according to the WHO Clinical Improvement Scale (change period: 28 days).
6. The proportion of participants with each of the scores (0-8) according to the WHO Clinical Improvement Scale (change period: 2 months).
7. Duration of symptoms of the disease of study participants who had acute respiratory viral infections, including COVID-19 (change period: 2 months).
8. The duration of the symptoms of the disease of the study participants who were infected with ARVI, including COVID-19 (measurement period: 28 days).

Confirmation of clinical cases of ARVI, including COVID-19:

In the following cases:

- 1) a positive result of PCR on SARS-CoV-2 RNA, regardless of the presence of clinical symptoms;
- 2) appearance of clinical symptoms of ARVI in the absence of a PCR result on SARS-CoV-2 RNA or in the case of a negative result on SARS-CoV-2 RNA, -

at any stage during participation in the study, a completion visit (Visit 3) is conducted at the end of the quarantine period (at least 14 days from the date of signing Consent for the treatment of a new COVID-19 coronavirus infection in outpatient settings (at home) and compliance with the isolation regime or discharge from the hospital in case of laboratory confirmation of COVID-19), at which the patient returns the participant's diary and reports his condition to the doctor-researcher, transmits information about hospitalization, duration of symptoms, results of tests and performed studies.

Definition of the COVID-19 case:

Suspicious case of COVID-19

Body temperature above 37.5° in addition to one or more of the following signs (in the absence of other known causes that explain the clinical picture, regardless of the epidemiological history):

- Cough (dry or with scant sputum)
- Shortness of breath
- Feeling of congestion in the chest
- SpO₂ no more than 95%
- Sore throat
- Nasal stuffiness or moderate rhinorrhea
- Smell disorders or anosmia
- Ageusia
- Conjunctivitis
- Fatigue

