- Myalgia
- Headache
- Vomiting
- Diarrhea
- Skin rash

Probable case of COVID-19

Body temperature above 37.5° in addition to one or more of the following signs:

- Cough (dry or with scant sputum)
- Shortness of breath
- Feeling of congestion in the chest
- SpO₂ no more than 95%
- Sore throat
- Nasal stuffiness or moderate rhinorrhea
- Smell disorders or anosmia
- Ageusia
- Conjunctivitis
- Fatigue
- Myalgia
- Headache
- Vomiting
- Diarrhea
- Skin rash

In the presence of at least one of the epidemiological signs:

- Return from cross-border travel 14 days before the onset of symptoms
- The presence of close contacts over the past 14 days with a person under surveillance for COVID-19, who subsequently became ill
- The presence of close contacts over the past 14 days with a person who has laboratory confirmed diagnosis of COVID-19

- The presence of professional contacts with persons who have a suspected or confirmed case of COVID-19

Or in combination with characteristic changes in the lungs according to computed tomography (CT), regardless of the results of a single laboratory test for the presence of SARS-CoV-2 RNA and an epidemiological history.

Also, a possible case of COVID-19 should include a clinical case in the presence of the clinical manifestations described above (fever in combination with one or more signs) with characteristic changes in the lungs according to imaging studies if it is impossible to conduct a laboratory study for the presence of SARS-CoV-2 RNA.

Confirmed case of COVID-19

A positive result of laboratory test for the presence of SARS-CoV-2 RNA using nucleic acid amplification methods or SARS-CoV-2 antigen using immunochromatographic assay regardless of clinical manifestations, or a positive result for IgA, IgM and/or IgG antibodies in patients with clinically confirmed COVID-19 infection.

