In the case of ARVI symptoms characteristic of a suspicious case of COVID-19, accompanied by a negative result of PCR test, registered during or after a preventive course (during the period of participation in the study after randomization until the end of the observation period), the patient may additionally undergo a quantitative test for the presence of IgM and IgG antibodies to SARS-CoV-2 by the ELISA method for the purpose of additional verification and detection of COVID-19 cases. An additional quantitative test for antibodies to SARS-CoV-2 can be performed from the 10th to the 21st day after the appearance of the first symptom of ARVI to register the immune response of the acute phase of infection at the beginning of its development (increased IgM levels) or during high-grade response (increased IgM and IgG), considering the seronegative the period of the disease (5-7 days). The analysis is taken only in the absence of fever and a satisfactory general condition of the patient, accompanied by a favorable recovery dynamics. When interpreting the results, it is necessary to consider the probability of obtaining false positive results (for example, the presence of "cross-reacting" antibodies). If the interpretation of the results is difficult, it is allowed to conduct a repeated ELISA study using the same test systems after 5-7 days to assess the dynamics of indicators. Quantitative determination of IgM and IgG antibodies in the blood by the ELISA method will be carried out with the support of DiaLab LLC Plus."

The condition of the study participant is assessed according to the WHO standard scale of clinical improvement from 0 to 8 points at each visit, including a phone call visit. In case of registration of ARVI at the final visit 3, in parallel with the current assessment of the participant's condition, an additional assessment of the case is carried out according to the WHO scale, reflecting the maximum clinical manifestation of the disease.

WHO Clinical Improvement Scale

| Assessment on the WHO scale | 0 | 1 | 2 | 3 | 4 | 5 | 6 | 7 | 8 |
|--|---|--------------------------|-----------------------|---------------------------------|--|---|--|---|-------|
| Select the appropriate score from 0 to 8 | Not infected | Outpatient | | Hospitalized with mild form | | Hospitalized with severe form | | | Died |

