3. EVALUATION OF EFFECTIVENESS PARAMETERS

3.1. Endpoints of the study

The primary criterion of effectiveness is the proportion of patients with acute respiratory viral infections, including COVID-19, at the end of the period of preventive administration of the drug (measurement time: 28 days).

The scientific hypothesis is that the prophylactic administration of Ingaron will lead to a decrease in the incidence of acute respiratory viral infections, including COVID-19, among adult volunteers.

The preventive efficacy of the study drug will be evaluated by the following primary and secondary endpoints.

Primary endpoint:

The proportion of patients with acute respiratory viral infections, including COVID-19, at the end of the period of preventive administration of the drug (measurement time: 28 days).

Secondary endpoints:

1. The proportion of patients with confirmed COVID-19 at the end of the period of preventive treatment of the drug (measurement period: 28 days).
2. The proportion of patients with acute respiratory viral infections, including COVID-19, at the end of the follow-up period (change period: 2 months).
3. The proportion of patients with confirmed COVID-19 at the end of the follow-up period (change period: 2 months).
4. Frequency of development of complicated course of ARVI.
5. The proportion of participants with each of the scores (0-8) according to the WHO Clinical Improvement Scale (change period: 28 days).
6. The proportion of participants with each of the scores (0-8) according to the WHO Clinical Improvement Scale (change period: 2 months).
7. Duration of symptoms of the disease of study participants who had acute respiratory viral infections, including COVID-19 (change period: 2 months).
8. The duration of the symptoms of the disease of the study participants who were infected with ARVI, including COVID-19 (measurement period: 28 days).

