- Frequency of development of complicated course of ARVI.

The proportion of patients will be presented as a frequency, a percentage in % indicating a bilateral 95% CI, measured according to the data recorded at the time of the corresponding measurement period. For a comparative analysis of the proportions between the groups, method of a two-sided version of the Fisher's exact test (with expected frequencies less than 5) or the Pearson chi-squared test ($2\chi^2$) (with the Yates correction for expected frequencies more than 5, but less than 10) will be used.

The analysis of secondary performance parameters will be carried out both on the ITT population (main analysis) and on the PP population (additional analysis).

Analysis of safety parameters

The study plans to analyze the following security variables:

- frequency of AE/SAE registration in treatment groups (in general and by organ systems);
- changes in vital signs (heart rate, blood pressure, body temperature, respiration rate and SpO₂) during the study (by visits and groups).

For categorical safety indicators in each group and for each visit, according to the survey scheme of participants, frequency, percentage in% and bilateral 95% CI will be calculated. Comparing groups by categorical indicators with the number of categories less than 5, Fisher's exact test will be used, otherwise Pearson chi-squared test (χ^2) will be used (with Yates correction for expected frequencies of more than 5, but less than 10).

The results of measuring vital signs (assessment of heart rate, respiration rate, blood pressure, body temperature and SpO₂) will be presented by treatment groups using descriptive statistics.

The analysis of safety parameters will be carried out on the safety population.

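### The 28-day confirmed-COVID-19 endpoint depends on unstandardised testing in an open-label trial, and the SAP has no rule or table row for ill participants without a timely test

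*Protocol*

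**What the plan says.** **Scheduled tests.** In the Protocol's Schedule of research procedures, the row "Analysis for RNA to SARS-CoV-2" is marked at Visit 0 and Visit 3 only. Visit 2, where the 28-day outcome is assessed, is a telephone call.

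**Illness during the study.** The Protocol (Confirmation of clinical cases of ARVI) and SAP 3.2 list two ways to become a case: a positive PCR with or without symptoms, or "appearance of clinical symptoms of ARVI in the absence of a PCR result on SARS-CoV-2 RNA" (or with a negative one). Neither document requires a test when symptoms begin.

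**Antibody test.** For symptoms that fit a suspicious case and come with a negative PCR, "the patient may additionally undergo a quantitative test for the presence of IgM and IgG antibodies", between the 10th and 21st day after the first symptom.

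**Confirmed case.** The definition asks for "A positive result of laboratory test for the presence of SARS-CoV-2 RNA using nucleic acid amplification methods or SARS-CoV-2 antigen", or positive antibodies in a clinically confirmed case.

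**Analysis.** SAP 5.1 (Secondary Endpoint analysis) takes proportions as "measured according to the data recorded at the time of the corresponding measurement period". SAP 5.3 uses available information only, without filling in. Tables 9 and 11 give a COVID-19 total split into confirmed, probable and suspicious, as n/N under the total number of subjects. They have no row for cases not tested. SAP 2.3 states that the study is open-label.

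**The concern.** Secondary endpoint 1 compares the proportion with confirmed COVID-19 at 28 days. Confirmation needs a laboratory result, but between screening and Visit 3 the plan neither schedules one nor ties one to symptoms. Whether an ill participant is tested is left to routine care and to the choices of participants and doctors who know the allocation.

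If the arms differ in how often ill people are tested, the confirmed proportions differ even when infection does not. If both arms are under-tested equally, the ratio is unbiased but power is lost. As the tables stand, a reader of the report could not tell a drug effect from a testing effect. COVID-19 is named in the trial's title, so a difference on this endpoint is likely to be quoted.

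**Working it through.** **The plan's own figure.** There is none to reproduce. No sample size, power or expected testing share is given for confirmed COVID-19. The only input taken from the plan's calculation is 315 randomised per group (Protocol, Number of participants; SAP 5.2).

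**Can a case from Days 0–28 be confirmed by a study procedure?**
- Visit 2 is a phone call, so no sample is taken.
- The study ELISA is described only after a negative PCR, so a participant with no PCR is outside that route.
- The Visit 3 PCR is still due in an ill participant who is not already confirmed (Protocol, Nasopharyngeal smear, waives it only for confirmed cases). It follows quarantine, however, and the Protocol's Introduction says the virus is well detected in a throat smear in the first week. It cannot reliably detect, or date, an infection from Days 0–28.
- What remains is testing outside the schedule, which is accepted but not standardised.

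**Size of a possible bias.** Assumptions, none given in the documents: no drug effect, the same true COVID-19 rate *c* in both arms, and a share *s* of infected participants tested and found positive.

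Observed confirmed rate = *c* × *s*. For *c* = 4%, *s* = 50% in Group I and 80% in Group II:
- Group I: 4% × 0.50 = 2.0%, or 315 × 0.020 = 6.3 expected cases
- Group II: 4% × 0.80 = 3.2%, or 315 × 0.032 = 10.1 expected cases
- Apparent relative reduction: 1 − 2.0/3.2 = 37.5%

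**How often would this be significant?** All pairs of binomial counts with 315 per arm were enumerated and passed through the SAP 5.1 rule (Fisher if an expected count is below 5, Yates if 5 to 10, otherwise Pearson; two-sided 0.05).

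| True rate, both arms | All tested | 50% vs 80% tested |
|---|---|---|
| 1% | 1.3% | 1.1% |
| 2% | 2.4% | 4.4% |
| 4% | 4.7% | 11.2% |
| 5% | 5.1% | 16.0% |

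At a true rate of 5%, other splits give 9.3% (60% vs 80%) and 26.7% (40% vs 80%). Swapping the shares between arms gives the same rates with the apparent effect reversed.

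**Equal under-testing.** With 50% tested in both arms and a true 5% versus 2%, the ratio is unbiased, but power under the same rule falls from 0.52 to 0.20.

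**The case against.** The strongest reply is that the plan already covers much of this. The primary endpoint counts symptomatic ARVI without any PCR. Tables 9 and 11 list probable and suspicious cases, so febrile untested participants can appear in the COVID-19 total. Tests in routine care are expected, and Visit 3 collects their results. All of this stands. It limits the point to the confirmed endpoints, but it does not standardise testing, and afebrile untested cases still fall outside every COVID-19 row.

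Four stronger readings are tempting, and the documents do not support them:
- *Untested ill participants are counted as non-cases by rule.* The SAP states no rule. The classification is inferred from the layout of Tables 9 and 11. If available information meant dropping the untested, the result would still depend on who was tested.
- *A result arriving after Day 28 cannot count.* The wording in SAP 5.1 is ambiguous. SAP 5.1 also says that ARVI case data are collected throughout the study, Visit 3 collects test results, and follow-up of ill participants may run to 90 days.
- *The 28-day and 2-month results are invalid because their test coverage differs.* The SAP compares arms within each time point and plans no comparison between the two.
- *The design produces a false COVID-19 effect.* Unequal testing is a risk in an open-label design, not something the documents show. Its direction is unknown.

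The illustration can also be challenged. A COVID-19 rate of 4% lies near the top of the Protocol's assumed 1–5% control incidence, which is for all ARVI. At 1–2% the error rate stays below 5%. Six versus ten cases gives a Fisher p of 0.45. That is why the working shows a range.

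**Conclusion.** The point holds for secondary endpoint 1. It holds more weakly for the 2-month confirmed endpoint, where the Visit 3 PCR gives both arms some common coverage. The primary endpoint does not depend on PCR.

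No SARS-CoV-2 test is scheduled or triggered by symptoms between screening and Visit 3, so confirmation rests on unstandardised testing with allocation known. The estimate could be biased either way. In the assumed case of 4% COVID-19 in both arms and 50% versus 80% tested, the confirmed rates are 2.0% versus 3.2% with no drug effect. This is significant in about 11% of trials, against 4.7% with full testing. With the same testing shares the figure runs from about 1% at a true rate of 1% to 16% at 5%. The true rates and testing shares are assumptions.

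This should be corrected in the SAP because it affects what can be concluded about COVID-19. It does not undermine the primary analysis.

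**What to change.** In SAP 5.1 and Tables 9 and 11:

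1. Report, by arm, how many ARVI cases had a PCR or antigen result, or an antibody result, from the illness.
2. Class ARVI cases without such a result as *COVID-19 status not determined*. Repeat the confirmed-COVID-19 comparison with all of them counted as COVID-19, then with none, and then with the two arm-opposed extremes (all in Group I and none in Group II, and the reverse).
3. Replace the phrase "measured according to the data recorded at the time of the corresponding measurement period" with a rule that assigns each case to the 28-day or 2-month window by date of first symptom, or by date of the positive sample if there were no symptoms, whenever the result arrives.
4. Show infections found only by the Visit 3 PCR in a separate row.

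The cost is SAP wording and a few table rows. No new visit or procedure is needed, since the diaries record symptom dates and Visit 3 collects test results. The downside is a wider range for the COVID-19 result, particularly because undetermined ARVI cases will include illnesses that were not COVID-19.
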